9 STUDY POPULATION

9.1 Inclusion Criteria

Eligible subjects must meet all the following criteria:

1. Male or female subjects ≥ 18 years of age at Screening.
2. Able and willing to comply with all study procedures.
3. Stable kidney function per Investigator assessment and no known episodes of AKI during the preceding 4 weeks.
4. Scheduled to undergo non-emergent cardiac surgery requiring cardiopulmonary bypass (CPB), which must include one of the following:
 - CABG alone;
 - Combined CABG and cardiac valve(s) replacement or repair;
 - Cardiac valve(s) replacement or repair alone.
5. Female and male subjects of childbearing potential must agree to use 2 forms of contraception, with at least 1 being a barrier method, or abstain from sexual activity for 30 days following study drug administration.
6. Male subjects must agree not to donate or sell sperm for 30 days following study drug administration.

9.2 Exclusion Criteria

Subjects will be ineligible for study participation if they meet any of the following criteria:

1. Presence of AKI at the time of Screening, as determined by the Investigator.
2. Surgery to be performed without cardiopulmonary bypass (CPB).
3. A significant portion of the surgery to be performed under conditions of circulatory arrest or hypothermia with rectal temperature $< 28^{\circ}\text{C}$ (82.4°F), as determined by the Investigator in consultation with the Medical Monitor.
4. $\text{eGFR} \leq 20 \text{ mL/min/1.73m}^2$ or need for dialysis.
5. Surgery for aortic dissection or to correct a major congenital heart defect.
6. Administration of iodinated contrast media within 24 hours prior to cardiac surgery or evidence of contrast-induced nephropathy prior to cardiac surgery.
7. Cardiogenic shock or hemodynamic instability within the 24 hours prior to surgery and requirement for inotropes or vasopressors or other mechanical devices, such as intra-aortic balloon counter-pulsation.
8. Requirement for any of the following within 7 days prior to cardiac surgery:
 - Defibrillator or permanent pacemaker;
 - Mechanical ventilation;

- Intra-aortic balloon counter-pulsation;
 - Left ventricular assist device;
 - Other forms of mechanical circulatory support.
9. Known history of cancer within the past 2 years, except for carcinoma in situ of the cervix or adequately treated non-melanoma cancer of the skin.
 10. Known or suspected sepsis at time of Screening or confirmed or treated endocarditis within 30 days prior to cardiac surgery.
 11. Other current active infection requiring systemic antibiotic treatment.
 12. Abnormal hepatic function, defined as total bilirubin or alanine aminotransferase or aspartate aminotransferase >2X the upper limit of normal at time of Screening or Child Pugh Class C liver disease or higher.
 13. Congenital coagulation disorder associated with a high risk of excessive bleeding or thrombosis per Investigator assessment.
 14. Asplenia (anatomic or functional)
 15. History of photosensitivity or active skin disease that, in the opinion of the Investigator, could be worsened by RBT-1.
 16. Known hypersensitivity or previous anaphylaxis to SnPP or any tin-based product.
 17. Serum ferritin >500 ng/mL or those who have received IV iron within 14 days of Screening.
 18. Pregnancy or lactation.
 19. Treatment with an investigational drug or participation in an interventional study within 30 days prior to administration of study drug.
 20. In the opinion of the Investigator, any disease processes or confounding variables that would inappropriately alter the outcome of the study.
 21. Inability to comply with the requirements of the study protocol.

9.3 Study Design

[figure not shown]
This is a Phase 2, multicenter, double-blind, randomized, placebo-controlled study to evaluate the effect of RBT-1 on preconditioning response biomarkers in subjects who are at risk for AKI following cardiac surgery. Eligible subjects will be randomized to receive a single dose of low-dose RBT-1 (45 mg SnPP/240 mg FeS), high-dose RBT-1 (90 mg SnPP/240 mg FeS), or placebo (normal saline) via IV infusion over a 120-minute period ≥ 24 but ≤ 48 hours prior to scheduled cardiac surgery.

All subjects will be assessed through Day 90 post-cardiac surgery. Subjects will be evaluated at Screening, 48 and/or 24 hours prior to surgery depending on the time of dosing, on Day 1 (day of surgery) and daily through Day 7 or Discharge if earlier, as well as on Days 30, 60, and 90, as described in the Event Schedule (see [Section 5](#)).

Assessments include biomarkers of preconditioning response and tubular injury, urine

output, incidence and severity of AKI, serum creatinine, days on ventilator, days in ICU, hospital length of stay, readmission rate, and safety (physical examination, clinical laboratory assessment, vital signs, concomitant medications, and adverse events). Evaluations for MAKE (death, need for dialysis, and change in kidney function) and safety will be performed through Day 90, as described in the Event Schedule (see Section 5).

The duration of the study will be approximately 90 days per subject. A schematic of the study design is presented below:

AKI = acute kidney injury; FeS = iron sucrose; h = hour; SnPP = stannous protoporphyrin

9.3.1 Stopping Rules

There are no pre-established stopping rules for this study.

9.4 Recordkeeping and Monitoring

All subject data will be reported in the electronic data capture system, except for central laboratory reports, which will be uploaded by electronic transfer by the central laboratory. All original source documents should be available for periodic monitoring and/or retrieval by a Sponsor representative designee. The Investigator is responsible for the accuracy of all data entered in the electronic case report forms (eCRFs) and for the timely completion of the eCRFs. The supporting documentation will be maintained at the site for a minimum of either:

1. Two (2) years following the approval of RBT-1 for this indication by the Food and Drug Administration (FDA)

or

- Two (2) years following notification by the Sponsor to the FDA of the termination of the entire investigation.

The Sponsor must be contacted and give written authorization prior to any study records being destroyed at investigative sites.

This study will be conducted in compliance with Good Clinical Practice (GCP), which includes the Sponsor- and IRB/IEC-approved protocol and ICF and the FDA and International Council for Harmonisation (ICH) regulatory guidelines and requirements. No changes will be made without prior approval unless it is imperative for subject safety. Any such departures from the protocol will be reported immediately to the Sponsor and relevant IRB/IEC.

All subjects' medical records and study-related documents will be made available to the Sponsor for regular monitoring and audits, as well as to the IRB/IEC and FDA or other governmental agency with oversight or compliance responsibilities for assuring subject rights and welfare.

9.5 Investigational Product

Subjects will be randomized to receive a single dose of double-blind RBT-1 (low-dose RBT-1 [45 mg SnPP/240 mg FeS] or high-dose RBT-1 [90 mg SnPP/240 mg FeS]) or placebo (normal saline).

9.5.1 Study Drug Description

The investigational product (RBT-1) is a combination of SnPP in a solution of sodium hydroxide and of FeS in a saline solution buffered with sodium bicarbonate.

Commercially available 0.9% sodium chloride (normal saline) for injection will be used for placebo administration at study sites.

9.5.2 Packaging

RBT-1 will be supplied as a sterile liquid (in separate vials of SnPP and FeS) for IV injection and is intended for single use. Glass vials of 5 mL are plugged with Teflon-coated rubber stoppers and sealed with aluminum seals.

9.5.3 Investigational Product Dispensing

All investigational products will be dispensed by designated and trained site pharmacy staff.

9.5.4 Dosage Preparation and Administration

Detailed instructions for dose preparation will be specified in the Pharmacy Manual.

Study drug (RBT-1 or placebo) will be administered via IV infusion over a 120-minute period ≥ 24 but ≤ 48 hours prior to scheduled cardiac surgery. Study drug administration may be performed in an outpatient setting.

Subjects will be observed for signs and symptoms of hypersensitivity during study drug administration and for at least 30 minutes after administration. Subjects should be

observed until they are deemed clinically stable. RBT-1 will only be administered when personnel and therapies are available for the treatment of any infusion-related reactions.

9.5.5 Storage Requirements

RBT-1 should be stored at controlled room temperature conditions (15 - 30°C/59 - 86°F) and protected from light.

9.5.6 Investigational Product Accountability

The Investigator or designee is responsible for maintaining accurate records accounting for the receipt, dispensing, and final disposition of all investigational products using the appropriate investigational product logs provided by the Sponsor.

9.5.7 Retrieval and Destruction

Periodically throughout the study, sites will perform investigational product reconciliation on a per-subject basis. The Sponsor's site monitor will review the log and once any discrepancies have been resolved, authorize destruction/disposition of the supplies associated with a given subject by signing the reconciliation log and will witness the destruction/disposition.

9.6 Randomization and Blinding

Each subject will be assigned an identification number by the site after the subject provides written informed consent.

The identification number will consist of a 7-digit number:

- The first 4 digits will designate the site number as assigned by the Sponsor.
- The last 3 digits will designate the order of the subject at that site.

The first subject who signs the ICF at the site is assigned the identification number 001, the second subject who signs the ICF is assigned 002, the third is assigned 003, etc. The subject will maintain the same identification number throughout the entire study. If a subject signs the ICF but does not meet the inclusion/exclusion criteria, the subject will be marked as a screen failure on the Screening and Enrollment Log provided by the Sponsor and will be entered in the electronic data capture system as a screen failure.

If the subject qualifies for study entry after Screening, the site staff will use the Interactive Web Response System (IWRS) to obtain the subject's randomized, double-blinded treatment assignment.

9.7 Study Visits

9.7.1 Screening (Within 30 Days Prior to Visit 1)

Study candidates will be evaluated for study entry according to the stated inclusion and exclusion criteria (Sections 9.1 and 9.2, respectively). The following procedures will be performed during Screening to establish each candidate's eligibility for enrollment into the study:

- Obtain signed, written informed consent. The informed consent must be signed before any procedures are performed.

- Record demographic information.
- Record medical history.
- Record concomitant medications.
- Perform physical examination, including weight and body mass index.
- Record vital signs.
- Obtain urine sample for pregnancy testing of female subjects of childbearing potential.
- Obtain blood samples for serum chemistry and hematology testing.
- Assess serum ferritin if not already included in the local laboratory chemistry panel.
- Obtain urine sample for urinalysis.

The Investigator will evaluate the results of all examinations, including clinical laboratory tests, and determine each candidate's suitability for the study according to the eligibility criteria.

Screening and dosing can occur on the same day if all pre-dose assessments completed and evaluated prior to dosing. However, if Screening and dosing occur on the same day, blood and urine samples will need to be collected for central laboratory analysis prior to dosing, as would be done on Visit 1a.

Physical examinations and routine labs (serum chemistry, hematology, urinalysis) performed as part of standard of care within 1 month of dosing administration (Visit 1a) can be used for Screening assessments.

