- 4 Hematology parameters include red blood cell count [RBC], hemoglobin, hematocrit, mean corpuscular volume [MCV], mean corpuscular hemoglobin [MCH], mean corpuscular hemoglobin concentration [MCHC], platelets, mean platelet volume [MPV], red cell distribution width [RDW], white blood cell count [WBC], and WBC differential (including neutrophils [absolute and percentage], lymphocytes [absolute and percentage], monocytes [absolute and percentage], eosinophils [absolute and percentage], and basophils [absolute and percentage]).
- 5 Urinalysis parameters include glucose, ketones, leukocytes, nitrite, blood, pH, protein, specific gravity, and reflex microscopic.
- 6 Urine output will be measured through Day 3.
- 7 Blood biomarkers include preconditioning response biomarkers (plasma heme oxygenase-1 [HO-1], ferritin, and interleukin-10 [IL-10]) and other biomarkers of RBT-1 activity and kidney function.
- 8 Blood and urinary biomarkers will be collected within 4 hours prior to cardiac surgery.
- 9 Urinary biomarkers include tubular injury biomarkers (kidney injury molecule-1 [KIM-1], cystatin C, and neutrophil gelatinase-associated lipocalin [NGAL]), and other biomarkers of RBT-1 activity and kidney function.
- 10 A pregnancy test will be performed in female subjects of childbearing potential.
- 11 RBT-1 and placebo will be administered via intravenous infusion over a 120-minute period.
- 12 Adverse events assessment will include photosensitivity assessment.

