9.7.2 Visit 1a

The following procedures will be performed prior to dosing:

- Re-confirm subject's eligibility to participate in the study.
- Record concomitant medications.
- Perform physical examination.
- Record vital signs.
- Obtain blood samples for serum chemistry, hematology, and blood biomarker testing.
- Obtain urine sample for urinary biomarker testing.
- Access the IWRS to obtain the subject's randomized, blinded treatment assignment (see [Section 9.6](#)).

Once all pre-dose procedures have been completed:

- Study drug (RBT-1 or placebo) will be administered via IV infusion over a 120-minute period under the supervision of the Investigator/designee. The date,

rate of infusion, total volume of infusion, and start/stop times of dosing will be recorded.

- Solicit any adverse events.

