9.7.6 Visit 9 (Day 30)

Subjects will return to the site on Day 30 for the following procedures:

- Record changes in concomitant medications.
- Perform physical examination.
- Record vital signs.
- Obtain blood samples for serum chemistry and hematology.
- Obtain urine sample for urinalysis.
- Obtain urine sample for pregnancy testing in female subjects of childbearing potential.
- Solicit any adverse events.

Note that the Day 30 visit may be conducted remotely as a virtual visit if an in-person visit is not possible. If a virtual visit is conducted: 1) blood and urine samples may be collected by remote phlebotomy, such as through a mobile phlebotomist or other blood collection center, and 2) the physical examination can be symptom-directed.

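### Pregnancy is excluded and eligibility is re-confirmed at Visit 1a, but the only pre-dose pregnancy test is at Screening, so an unrecognised pregnancy can pass every listed check when Screening was on an earlier day

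*Protocol*

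**What the plan says.** Exclusion 18 (protocol Section 9.2, repeated in the synopsis) reads "Pregnancy or lactation" and carries no time qualifier. At Visit 1a, before dosing, protocol Section 9.7.2 instructs the site: "Re-confirm subject's eligibility to participate in the study".

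The pregnancy test appears at two visits:

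- **Screening** (protocol Section 9.7.1, a window of up to 30 days before Visit 1): "Obtain urine sample for pregnancy testing of female subjects of childbearing potential".
- **Day 30** (protocol Section 9.7.6): "Obtain urine sample for pregnancy testing in female subjects of childbearing potential".

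The visit schedule in SAP Appendix A marks the same two visits, 0 and 9. Footnote 10 to the protocol's Section 5 schedule says only who is tested ("A pregnancy test will be performed in female subjects of childbearing potential") and adds no time point.

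The urine collected at Visit 1a has a different stated purpose: "Obtain urine sample for urinary biomarker testing". Inclusion 5 (protocol Section 9.1) asks subjects of childbearing potential to agree to two contraceptive methods, one of them a barrier, or to "abstain from sexual activity for 30 days following study drug administration". Protocol Section 9.8 sends Screening samples to a local laboratory and all other samples to a central one, and it names pregnancy testing among the laboratory parameters it covers.

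**The concern.** Pregnancy status can change without anyone noticing between Screening and Visit 1a, which is not true of a history item such as asplenia. The protocol treats pregnancy as disqualifying and asks for eligibility to be confirmed again on the day of dosing, but it lists nothing at that visit that would reveal an unrecognised pregnancy. It also does not say what contraception or abstinence applies between the Screening test and the infusion.

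The stake is subject safety: a fetus could be exposed to an investigational porphyrin given with intravenous iron. The chance is 2 in 3 for any one subject, since two of the three equally sized arms are active. Section 10 of the protocol counts a congenital anomaly as a serious outcome but ends adverse event recording at Day 90, and the text available for review describes no follow-up of an exposed pregnancy. Protection therefore rests mainly on not dosing.

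**Working it through.** The plan gives no figure for this point. The check sets the passages side by side and works out two intervals.

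**1. Interval from the pre-dose test to dosing.** Screening may be up to 30 days before Visit 1 (protocol Section 9.7.1), and dosing is at Visit 1a. The same section allows Screening and dosing on one day. The interval therefore runs from 0 days to 30 days. The allowance for using standard-of-care results from the preceding month covers the physical examination, serum chemistry, hematology and urinalysis. It does not name the pregnancy test, so it does not alter this range.

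**2. Interval from dosing to the next scheduled test.**
- Dosing is 24 to 48 hours before surgery, which is 1 to 2 days.
- Surgery is on Day 1 (SAP Section 4.2). If Day 30 is 29 days after surgery, the interval is 29 + 1 = 30 to 29 + 2 = 31 days. If Day 30 is read as 30 days after surgery, it is 30 + 1 = 31 to 30 + 2 = 32 days. Together: 30 to 32 days.
- SAP Appendix A gives the Day 30 visit a window of ±3 days: 30 − 3 = 27 to 32 + 3 = 35 days.

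**3. What Visit 1a could detect.** The pre-dose list in protocol Section 9.7.2 holds the eligibility re-check, concomitant medications, physical examination, vital signs, blood for chemistry, hematology and biomarkers, urine for biomarkers, and access to the randomization system. The chemistry and hematology parameters in the footnotes to Section 5 include no pregnancy marker. A pregnancy that the subject knows of or reports would be caught by the eligibility re-check. An unrecognised one has no listed step that would find it.

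**4. What inclusion 5 covers before dosing.** The sentence can be read in two ways. The 30 days after dosing may govern both contraception and abstinence, or abstinence alone, which leaves contraception with no stated start or end. Neither reading gives a start before dosing.

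**5. Whether another passage closes the gap.** The other visit lists (protocol Sections 9.7.3 to 9.7.5, 9.7.7 and 9.7.8) contain no pregnancy test, and the SAP adds none.

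**The case against.** The strongest reply is that the protocol does act on pregnancy at dosing. Exclusion 18 is not limited to Screening, whereas exclusions 1, 10 and 12 tie conditions to that visit, and both the visit list and SAP Appendix A put an eligibility check at Visit 1a. A reader might infer from the test schedule that a woman who conceives after Screening counts as eligible. The documents do not support that: she is ineligible, and a known, suspected or reported pregnancy must stop dosing. This limits the point to unrecognised pregnancies. It does not remove it, because re-confirmation without a test cannot find those.

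A reader might also infer that contraception is required only after dosing. That is one reading of an ambiguous sentence. What stands is that no pre-dose start is stated.

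Nor should 30 days be taken as the usual gap. It is the maximum, and the documents do not say how often Screening and dosing will fall on the same day.

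Finally, it is fair to say that passing the Visit 1a biomarker urine to a pregnancy test is not an obvious cure. Under Section 9.8 that sample goes to the central laboratory, and nothing says a result would return before the infusion. A repeat test would also share the first one's inability to detect a very early pregnancy. It would shorten the unprotected interval without abolishing it. These objections bear on the remedy and the grade; the mismatch between exclusion 18 and the test schedule remains.

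**Conclusion.** The point holds in a limited form. When Screening was on an earlier day than dosing, a pregnancy that began or became detectable after the Screening test, and that the subject does not know of, passes every check listed before the infusion. The untested interval is 0 to 30 days, and the next scheduled test comes about 27 to 35 days after dosing. Earlier detection outside the protocol is possible.

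Frequency cannot be estimated. The trial plans about 126 subjects, and the number of women of childbearing potential is not given. It is assumed to be small in a bypass and valve surgery population, but the criteria admit women from 18 years, including those having valve surgery alone. No efficacy endpoint or analysis depends on this. It is a safety gap worth closing because the remedy is small, not because many subjects are likely to be affected.

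**What to change.** The sponsor should reconcile exclusion 18, inclusion 5, the Visit 1a procedures in protocol Section 9.7.2, the Section 5 schedule, SAP Appendix A and the laboratory rule in protocol Section 9.8. Two results are needed:

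- The Visit 1a eligibility re-check can actually be carried out for pregnancy in women of childbearing potential, with a result available before dosing. One possible route is to schedule the protocol's existing urine test at Visit 1a with local reading. Section 9.8 would then need an exception.
- Inclusion 5 says plainly what applies between Screening and dosing, and whether its 30 days govern contraception as well as abstinence. The length of any contraception period is for the sponsor to set.

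If the sponsor takes that route, the cost is one more urine test in a subgroup that is probably small, a local-reading exception in Section 9.8, and matching edits to the two schedules. The documents do not say whether sites hold a test that can be read on the spot, so the sponsor should confirm that before settling on it.

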9.7.2 Visit 1a

The following procedures will be performed prior to dosing:

- Re-confirm subject's eligibility to participate in the study.
- Record concomitant medications.
- Perform physical examination.
- Record vital signs.
- Obtain blood samples for serum chemistry, hematology, and blood biomarker testing.
- Obtain urine sample for urinary biomarker testing.
- Access the IWRS to obtain the subject's randomized, blinded treatment assignment (see [Section 9.6](#)).

Once all pre-dose procedures have been completed:

- Study drug (RBT-1 or placebo) will be administered via IV infusion over a 120-minute period under the supervision of the Investigator/designee. The date,

rate of infusion, total volume of infusion, and start/stop times of dosing will be recorded.

- Solicit any adverse events.

